# 7.2 Screening Visit

Prior to scheduling the screening visit, potentially eligible candidates for participation will have their medical records reviewed by one of the investigators. The following must be made available by the potential subject:

- 1. his/her age, gender, height, weight, age of diabetes onset, insulin type and requirements;
- 2. completed questionnaire inquiring for the presence of contraindicated medical conditions;
- 3. statement from his/her diabetologist regarding the type and stability of diabetes, the duration of the doctor-patient relationship, the current treatment regimen, blood pressure control, and presence of micro- or macrovascular complications (retinopathy, nephropathy, neuropathy, artherosclerosis), including their severity and treatment; and
- 4. recent (last 6 months) laboratory reports for HbA1c, urinary albumin, kidney and liver function, and fasting lipids.

If review of these materials indicates that the potential subject is not eligible, s/he will be notified by a study coordinator and explained why this is so (e.g. age > 65 years); if review indicates potentially unsuitable diabetes care, the potential subject will be referred to Penn's Rodebaugh Diabetes Center for further assessment and management; if review indicates that the potential subject may be eligible, s/he will be contacted by a study coordinator to schedule the screening visit.

At the screening visit, the study details and procedures will be discussed with a coordinator. If the potential subject remains interested, s/he will review the informed consent document with the coordinator, and an investigator will join the discussion and answer any questions. Once

satisfied that all questions have been answered, the potential subject will either decline to participate or sign the informed consent document. This may occur at a subsequent visit if the potential subject desires, in order to think further about what participation means and/or to consult with family and/or friends. If at any time the suitability of diabetes care is questioned, the potential subject will be referred to Penn's Rodebaugh Diabetes Center for further assessment and management.

Once informed consent has been obtained, eligibility will be confirmed through the performance of a history and physical examination (that includes a neurologic assessment), hypoglycemia and glycemic lability questionnaires, EKG, fasting serum biochemistries (glucose, c-peptide, electrolytes, creatinine, liver function tests [LFTs], and lipid panel), HbA1c, TSH, complete blood count (CBC, including WBC differential), coagulation studies (PT/INR, PTT, Fibrinogen), blood type, HLA type, panel reactive anti-HLA antibodies, serum HCG (females), serologies (HBV, HCV, HIV 1&2, EBV, HTLV 1&2), PPD, PSA (men over 40-years or with a family history of prostate cancer), Boost® stimulated serum glucose and c-peptide, urine collection for creatinine and albumin, chest X-ray, abdominal ultrasound, and cardiac persantine thallium of electrocardiogram. More than one visit will certainly be necessary to collect this information. Additional reports will be required from each subject's diabetologist, retinologist, dentist (to exclude infection), and gynecologist (indicating results of Pap smear and mammography for women older than 35 years). A psychosocial evaluation may be requested if either a coordinator or investigator is unsure whether a potential subject may be mentally unfit to undergo the procedure or to determine whether a psychosocial problem may be responsible for the instability of diabetes; such an evaluation would be performed by an experienced transplant social worker and/or psychiatrist. Subjects with a history or examination evidence of a central neurologic disease (e.g. multiple sclerosis) will be considered ineligible at Penn so that monitoring for neurologic warning signs of possible PML, such as changes in vision, loss of balance or confusion will not erroneously be attributed to an underlying neurologic condition. Once all eligibility criteria (inclusion and exclusion) are met, the subject will be placed on the transplant waiting list.

### 7.3 Baseline Visits

Once enrolled, subjects will return every 3months to assess the adequacy of their diabetes care, determine the HbA1c, and complete hypoglycemia and glycemic lability questionnaires in order to ensure continued eligibility for transplantation. Additional tests will be repeated as indicated in the timeline provided in the appendix.

Hypoglycemia will be assessed by completing 1) the Clarke survey of reduced hypoglycemia awareness, 2) the Ryan hypoglycemia score, and 3) the Hypoglycemia Fear Survey.

Glycemic lability will be assessed by calculating 1) the mean amplitude of glycemic excursions from 2 consecutive days of 7 blood glucose measurements each day, and 2) the Ryan lability index.

On one occasion (repeated annually as necessary), a hypoglycemic clamp will be performed to evaluate glucose counter-regulation after an overnight admission to the GCRC.

On one occasion (repeated annually as necessary), a continuous glucose monitoring system will be employed for 72-hours to assess the duration of hypo- and hyperglycemic episodes.

Insulin sensitivity will be assessed by a frequently-sampled intravenous glucose tolerance test (FSIGT) and euglycemic clamp. The euglycemic clamp will serve to validate the FSIGT-derived index of insulin sensitivity and provide normoglycemic control data for the hypoglycemic clamp. Both the FSIGT and a euglycemic clamp will be done annually, as will a hypoglycemic clamp. One clamp will be performed on the initial overnight GCRC admission. The remaining clamp will be done on the second overnight GCRC admission. The performance of the euglycemic clamp will occur in randomized order with the hypoglycemic clamp (above). Retinopathy will be evaluated by photography on an annual basis.

During this time of eligibility prior to transplant, additional baseline immunologic mechanistic assays will be performed as indicated in the timeline provided in the appendix. Their descriptions can be found in a subsequent section titled Mechanistic Assays.

#### 7.4 Randomization

Once a compatible islet prep becomes available, subject eligibility will be re-confirmed. Eligible subjects will be randomized on Day -2 relative to transplant, between CIT-05 and CIT-07. Subjects randomized will receive immunosuppressive therapy beginning on Day -2 (see Section 5 for full description of Study Treatment Regimen). Subjects will receive the initial islet transplant on Day 0 and will continue the immunosuppression regimen detailed in Section 5.

# 7.5 Study Treatment Visits

The first study treatment visit will occur at the time a suitable islet preparation is available for transplantation. Once a suitable donor pancreas becomes available, the potential recipient will be notified and requested to arrive promptly (< 2-hours) for admission to the Kidney/Pancreas Transplant service of the Hospital of the University of Pennsylvania. On admission, blood work (glucose, HbA1c, electrolytes, creatinine, LFTs, CBC and differential, PT/INR, PTT, blood type and cross-match [including to HLA antigens]), urinalysis, EKG (unless performed in last 3 months), and chest X-ray (unless performed in last 3 months) will be performed. Once subject eligibility is confirmed by the above tests and the islet preparation meets release criteria, the induction of immunosuppression will begin on Day -2 with the administration of Thymoglobulin  $^{\otimes}$   $\pm$  rituximab, and the islet preparation will remain in culture for  $\sim$  48-hours until infusion on Day 0. On Day 0, once the islet preparation has been determined to still meet release criteria, the subject will proceed to the operating room for the transperitoneal infusion of islets to the portal vein under general anesthesia.

The immunosuppression and islet transplants will be delivered during the hospitalization as detailed in the above section titled Study Design. Blood work will be monitored every 6-12 hours for 48-hours post-infusion for glucose, electrolytes, creatinine, LFTs, CBC and differential, and levels of tacrolimus and rapamycin. BG will be performed every 2-hours during 12-hours post-infusion and dextrose and/or insulin will be administered as needed to maintain the BG 100-140 mg/dL. Thereafter, BG will be performed at least 7 times daily and basal (for insulin pumps) or glargine insulin used at  $\sim 30-50$  % of the pre-transplant dose for fasting BG > 100 mg/dL, and bolus (lispro or aspart) insulin used before meals for post-prandial BG > 140 mg/dL.

Hospital discharge is anticipated by Day +2, after which four weekly followed by four biweekly clinic visits will occur for the first 3 months to monitor glucose, electrolytes, creatinine, LFTs, CBC and differential, and trough levels of tacrolimus and rapamycin, and to titrate insulin therapy based on prior week's 4-7 daily BG measurements (pre- and 2-hours post-meals and bedtime). BG targets will be < 110 mg/dL fasting and < 140 mg/dL after meals for the first month, followed by < 126 mg/dL fasting and < 180 mg/dL after meals thereafter. Insulinindependence (defined in Section 3.1.1) will be determined at  $75 \pm 5$  days post-transplant based in part on the ability to achieve those latter glycemic targets.

Subjects who do not meet the criteria for insulin-independence at any time after 75 days following the initial transplantation will be eligible for a second (or third) transplantation of islets from one or more donor pancreata, unless sensitization to donor antigen, as indicated by the development of >20% panel-reactive anti-HLA antibodies, has occurred. A similar procedure for hospital admission will be followed for a subsequent infusion of islets, except that daclizumab will replace Thymoglobulin® and start on Day 0; thus, no period of islet culture will be required. Post-infusion care will be identical for the first 2 months.

# 7.5.1 Criteria and Timing for Subsequent Islet Transplants

Islet transplant recipients who do not meet criteria for insulin independence (see section 3.1), but have either a basal or stimulated c-peptide level  $\geq 0.3$  ng/mL (0.1 nmol/L), will be considered **insulin-dependent with partial islet graft function**, and will be considered for a **second islet islet transplant**. Their insulin requirements will be determined by the total daily dose necessary to maintain the HbA1c  $\leq 7.0\%$ , the fasting capillary glucose level  $\leq 140$  mg/dL (7.8 mmol/L), and the 2-hour post-prandial capillary glucose levels  $\leq 180$  mg/dL (10.0 mmol/L), based on measuring capillary glucose levels a minimum of 21 times in a seven day period, and having at least one MAGE in that week.

In order to be eligible for a second islet transplant the following requirements must be met:

- 1. Subject received ≥5,000 IE/kg with the first transplant, but failed to achieve or maintain insulin independence
- 2. Subject has been compliant with study monitoring and prescribed immunosuppressive therapy
- 3. Subject has no unresolved SAEs
- 4. No evidence of progressive renal dysfunction, with blood creatinine rising above 2.0 mg/dL (177  $\mu$ mol/L)
- 5. No evidence of hypersensitization, allergic responses, or other potentially serious drug reactions to medications required by the protocol
- 6. PRA ≤50% by flow cytometry (assessment performed locally) and the alloantibody specificity not cross-reactive with antigen(s) present in the subsequent islet preparation in order to avoid unacceptable antigen(s).

A second islet transplant will be considered after the  $75 \pm 5$  days visit and metabolic assessment is completed, but before 8 months from the first transplant.

Islet transplant recipients who do not meet the criteria for insulin independence after the first infusion, and have both basal and stimulated c-peptide levels <0.3 ng/mL (0.1 nmol/L), will be considered for a second islet transplant only after review of the potency testing from the first transplant product and post-transplant clinical data by the Steering Committee that will have to give the final approval for the additional islet transplant.

If after the second islet transplant both basal and stimulated c-peptide levels remain <0.3 ng/mL (0.1 nmol/L), these recipients will be considered **failures** with no islet graft function, and immunosuppression will be withdrawn.

The option of a **third islet transplant** under this protocol will be considered only if all of the following conditions are met:

- 1. The subject received greater than 4,000 IE/kg with the second transplant, but remains dependent on insulin for longer than one month after the second transplant.
- 2. There is evidence of partial graft function.
- 3. The CIT PIs, Site PIs, and the Steering Committee have determined that there were no relevant protocol deviations at the site.
- 4. The subject has been compliant with study monitoring and prescribed immunosuppressive therapy.
- 5. No evidence of a serious and life-threatening infection, AE, or other condition that precludes attempting an intraportal injection or continuation of the post-transplant treatment regimen.
- 6. No evidence of PTLD.
- 7. No evidence of progressive renal dysfunction, with blood creatinine rising above 2.0 mg/dL (177  $\mu$ mol/L).
- 8. No evidence of hypersensitization, allergic responses, or other potentially serious drug reactions to medications required by the protocol.
- 9. No evidence of abnormal liver ultrasound and LFTs within 1.5 times the ULN range.
- 10. PRA <50 by flow cytometry (assessment performed locally) and the alloantibody specificity not cross-reactive with antigen(s) present in the subsequent islet preparation in order to avoid unacceptable antigen(s).

Subjects who have completed 8 months of follow-up post-first transplant will no longer be eligible for additional islet transplants funded under this protocol. Subjects that do not meet the criteria for a subsequent transplant and do not have a functioning graft will enter a reduced follow-up schedule (Appendix 2).

## 7.6 Follow-up Visits

At  $75 \pm 5$  days following each islet transplant, insulin-independence will be assessed as the primary endpoint as defined above (please see Section 3.1.1) based on one week of frequent capillary blood glucose monitoring ending with a fasting clinic visit for determination of HbA1c, fasting serum glucose and c-peptide, and serum glucose and c-peptide 90-minutes after ingestion of Boost®. This information also allows for the calculation of the  $\beta$ -score, a composite index of

islet graft function. Other self-glucose monitoring information captured at this visit will enable calculation of the Clarke and HYPO scores of hypoglycemia awareness and severity, respectively, the hypoglycemia fear survey, and the MAGE and LI scores of glycemic lability. This assessment will be repeated at 6, 9, 12, 15, 18, 21, and 24 months post-transplant.

The acute c-peptide and insulin responses to IV glucose and arginine will be performed during a two night admission to the GCRC scheduled at 3 months following each transplant, and at 12 and 24 months after the last transplant. The IV glucose test will be administered as a frequently-sampled intravenous glucose tolerance test in order to calculate insulin sensitivity ( $S_I$ ) and the disposition index (DI). The IV arginine test will be performed with glucose-potentiation in insulin-independent recipients and those taking  $\leq 0.1$  U/kg of daily insulin to optimize glycemic control in order to determine the  $\beta$ -cell secretory capacity at day 75 and at 12 months. Also at 3, 12, and 24 months, 72-hours of continuous glucose monitoring will be performed.

At 6 and 14 months post-transplant, paired hypoglycemic and euglycemic clamps will be performed one week apart, in randomized order, each after a one night admission to the GCRC.

At 12 months following the first transplant retinal photography will be performed.

Clinic visits for immunosuppression drug monitoring will occur monthly for the first two years and quarterly thereafter. Additional tests will be repeated as indicated in the timeline provided in the appendix.

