Intraportal delivery of islets isolated from cadaveric donors will be achieved using a transperitoneal approach through a mini-laparotomy. Islets will be ABO compatible and have a negative serum crossmatch for T lymphocytes, but HLA matching will not be required. It is estimated that >600,000 IEq will be required per recipient at an average of 9,000 IEq/kg of recipient body weight to achieve insulin independence. To optimize the chance of achieving insulin-independence with no more than two procedures, islet preparations  $\geq$ 5,000 IEq/kg will be used for the first infusion, and islet preparations  $\geq$ 4,000 IE/kg will be used for subsequent infusions. The quantity of tissue transplanted will be < 7 mL per infusion. Quality control testing will include assessment of islet purity (> 30%), viability (> 70%), sterility (negative gram stain), and endotoxin content (< 5 IU/kg recipient) prior to release. Functional assessment of islets will also be performed.

Islets will be infused together with heparin and ciproflaxin (70 U/kg) with periodic portal pressure monitoring. Heparin will be continued for 48 hours after the procedure as an intravenous drip with target PPT levels of 50-60 seconds. Following completion of heparin, subjects will be treated with enoxaprin 30 mg subcutaneously bid through day 7.

Subjects who do not meet criteria for insulin-independence at any time after 75 days following the initial transplantation may be eligible for a second transplantation of islets. If the development of panel-reactive anti-HLA antibodies has occurred, only subjects with a PRA ≤ 20% will remain eligible, and both antibody specific and prior mismatched antigens will be avoided. To avoid problems related to Thymoglobulin® sensitization, we will administer daclizumab (2 mg/kg on day 0 followed every two weeks with 1 mg/kg for 4 additional doses) in order to sustain an anti-T lymphocyte induction effect. Should a third infusion of islets occur to achieve insulin-independence, only if the interval between the second and third islet infusions is >10 weeks will an additional course of daclizumab be administered. Rituximab administration will not be repeated with either a second or third infusion of islets.

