#### 3.1.1 Secondary Endpoints

#### **Efficacy Endpoints**

At  $75 \pm 5$  days following the first and final transplant(s):

- The proportion of insulin-independent subjects
- The percent reduction in insulin requirements
- HbA1c
- MAGE
- LI
- Ryan hypoglycemia severity (HYPO) score
- Basal (fasting) and 90-min glucose and c-peptide derived from the mixed-meal tolerance test (MMTT)
- β-score
- C-peptide: (glucose X creatinine) ratio
- Acute insulin response to glucose (AIRglu), insulin sensitivity, and disposition index derived from the insulin-modified frequently-sampled IV glucose tolerance (FSIGT) test
- Glucose variability6 and hypoglycemia duration derived from the CGMS

• Quality of life (QOL) measures

If a third transplant occurs less than 75 days after the second transplant, the 75 day endpoint data for the second transplant will not be collected.

At  $365 \pm 14$  days following the first transplant

- The proportion of subjects with an HbA1c <7.0% at Day 365 AND free of severe hypoglycemic events from Day 28 to Day 365 inclusive
- The proportion of subjects receiving a second islet transplant
- The proportion of subjects receiving a third islet transplant

A severe hypoglycemic event is defined as an event with one of the following symptoms: memory loss; confusion; uncontrollable behavior; irrational behavior; unusual difficulty in awakening; suspected seizure; seizure; loss of consciousness; or visual symptoms, in which the subject was unable to treat him/herself and which was associated with either a blood glucose level <54 mg/dL [3.0 mmol/L] or prompt recovery after oral carbohydrate, IV glucose, or glucagon administration.

At  $365 \pm 14$  days following the first and final islet transplant:

- The proportion of insulin-independent subjects
- The percent reduction in insulin requirements
- HbA1c
- MAGE
- LI
- Clarke score
- HYPO score
- Basal (fasting) and 90-min glucose and c-peptide (MMTT)
- β-score
- C-peptide: (glucose X creatinine) ratio
- AIRglu insulin sensitivity, and disposition index derived from the FSIGT test
- CGMS
- OOL
- The proportion of subjects receiving a second islet transplant
- The proportion of subjects receiving a third islet transplant
- The rate of subjects with an HbA1c  $\leq$ 7.0% and free of severe hypoglycemic events)

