#### Safety Endpoints

At  $75 \pm 5$  days following each transplant and  $365 \pm 14$  days following the first and final islet transplant:

• The incidence and severity of AEs related to the islet transplant procedure including: bleeding (>2 g/dL decrease in hemoglobin concentration); segmental

- portal vein thrombosis; biliary puncture; wound complication (infection or subsequent hernia); and increased transaminase levels (>5 times upper limit normal [ULN])
- The incidence and severity of AEs related to the immunosuppression including: allergy; reduction in GFR; increase in urinary albumin excretion; addition or intensification of anti-hypertensive therapy; addition or intensification of anti-hyperlipidemic therapy; oral ulcers; lower extremity edema; gastrointestinal toxicity; neutropenia, anemia, or thrombocytopenia; viral, bacterial, or fungal infections; and benign or malignant neoplasms
- The incidence of a change in the immunosuppression drug regimen
- The incidence of immune sensitization defined by presence of anti-HLA antibodies absent prior to transplantation

At  $75 \pm 5$  and  $365 \pm 14$  days following the first islet transplant:

• The incidence of worsening retinopathy as assessed by change in retinal photography

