## 3.1.2 Additional Hypothesis Generating Endpoints:

At  $75\pm 5$  days following the second and third transplants, the following will be reported for the subset who receive a second transplant who also have data collected and also for the subset who receive a third transplant.

- the proportion of insulin-independent subjects
- the percent reduction in insulin requirements
- HbA1c
- MAGE
- LI
- HYPO score
- Basal (fasting) and 90-min glucose and c-peptide (MMTT)
- β-score
- C-peptide: (glucose X creatinine) ratio
- Acute insulin response to glucose (AIRglu), insulin sensitivity, and disposition index derived from the insulin-modified frequently-sampled intravenous glucose tolerance (FSIGT) test
- Glucose variability and hypoglycemia duration derived from the continuous glucose monitoring system® (CGMS)
- QOL

At  $365 \pm 14$  days following the last islet transplant will include the change in the following measures from the results obtained at  $75 \pm 5$  days following the last islet infusion:

- the proportion of insulin-independent subjects
- the percent reduction in insulin requirements
- HbA1c
- MAGE
- LI
- Clarke score
- HYPO score
- Basal (fasting) and 90-min glucose and c-peptide (MMTT)
- β-score
- C-peptide: (glucose X creatinine) ratio
- Glucose variability and hypoglycemia duration derived from the continuous glucose monitoring system® (CGMS)
- QOL

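### Three assessment timings contradict the non-primary endpoints they serve: FSIGT and CGMS in section 7.6, the Clarke score in Appendix 1, and Day 75 retinopathy in section 3.1.1

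*Protocol*

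**What the plan says.** **FSIGT, CGMS and arginine.** Under its heading for 75 ± 5 days after the first and final transplant, section 3.1.1 lists the acute insulin response to glucose, "insulin sensitivity, and disposition index derived from the insulin-modified frequently-sampled IV glucose tolerance (FSIGT) test", and also the CGMS measures of glucose variability and hypoglycemia duration. Section 7.6 says the glucose and arginine responses "will be performed during a two night admission to the GCRC scheduled at 3 months following each transplant", and adds: "Also at 3, 12, and 24 months, 72-hours of continuous glucose monitoring will be performed". The same paragraph says the glucose-potentiated arginine test serves to determine the β-"cell secretory capacity at day 75 and at 12 months". Section 3.1.3 gives the arginine test a window of 75 ± 15 days. Appendix 1 marks FSIGT, CGMS and the arginine test at Visit 10 (Day 75, ± 5). Section 9.1.2 refers the reader to Appendix 1 for the timing of all metabolic assessments.

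**Clarke score.** Section 3.1.2 says the endpoints at 365 ± 14 days after the last transplant "will include the change in the following measures from the results obtained at" 75 ± 5 days, and the Clarke score is on that list. Section 7.6 expects it to be calculable from the Day 75 visit. Appendix 1 does not mark it there.

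**Retinopathy.** Under 75 ± 5 and 365 ± 14 days after the first transplant, section 3.1.1 lists this safety endpoint: "The incidence of worsening retinopathy as assessed by change in retinal photography". The synopsis lists it at 365 ± 14 days only. Section 7.6 schedules photography at 12 months. Appendix 1 and its footnote on retinopathy provide photographs on the waiting list or at baseline, and at Y1.

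**The concern.** An endpoint tied to a study day needs an assessment scheduled on that day. In these three places one part of the protocol fixes the day and another part either moves the assessment or leaves it out.

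The consequence differs by item. A site that works from section 7.6 would collect FSIGT and CGMS outside the endpoint window. A site that works from Appendix 1 would collect no baseline for the Clarke change. For Day 75 retinopathy, no site would have data whichever section it followed. Section 10.2.2 does not impute missing secondary endpoints, and the trial has 12 subjects, so values that are mistimed or never collected cannot be made good in the analysis.

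**Working it through.** No figure in the plan needs reproducing. The check is date arithmetic and a reading of the Appendix 1 columns.

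**Step 1: does 3 months meet the Day 75 window?** Inputs are 3 months (section 7.6), ± 7 days counted from the calendar date of the transplant (section 7.7), and 75 ± 5 days (section 3.1.1).

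- Three calendar months last 89 to 92 days, depending on the starting month.
- Earliest visit: 89 − 7 = Day 82. Latest visit: 92 + 7 = Day 99.
- Endpoint window: 75 − 5 = Day 70 to 75 + 5 = Day 80.
- Smallest gap: 82 − 80 = 2 days. The windows do not overlap. (A flat 91 days would give Days 84 to 98 and a gap of 4, but section 7.7 counts by calendar date, so 2 is the figure to use.)
- Arginine window in section 3.1.3: 75 − 15 = Day 60 to 75 + 15 = Day 90. A 3-month visit falls inside it only at the upper edge, Days 82 to 90.

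Appendix 1 has no Month 3 visit: Day 75 is followed by Day 120.

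**Step 2: what does each source schedule?**

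| Assessment | Endpoint text | Section 7.6 | Appendix 1 marks |
|---|---|---|---|
| FSIGT | 75 ± 5 (3.1.1) | 3 months | Waiting list, Day 75, Day 365, Y1 |
| CGMS | 75 ± 5 (3.1.1) | 3 months | Waiting list, Day 75, Day 365, Y1 |
| Arginine test | 75 ± 15 (3.1.3) | 3 months, and also Day 75 | Day 75, Day 365 |
| Clarke | Change from 75 ± 5 to 365 ± 14 (3.1.2) | Day 75 | Screening, waiting list, Day 180, Day 365, Y1 |
| Retinal photograph | 75 ± 5 and 365 ± 14 (3.1.1) | 12 months | Waiting list or baseline, Y1 |

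The HYPO row of Appendix 1 does carry a Day 75 mark, so the gap in the Clarke row is not a general feature of the questionnaire-type measures.

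**Step 3: can the Day 75 Clarke score be recovered from other data?** Section 7.6 speaks of self-monitored glucose information from the Day 75 visit. Section 9.1.2.4 defines the Clarke survey as eight questions that the subject answers. Glucose records cannot supply those answers, so the form itself has to be completed at that visit.

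**The case against.** The strongest reply is that Appendix 1 already settles the first item. It schedules FSIGT, CGMS and the arginine test at Day 75 ± 5. Section 9.1.2 makes it the source for metabolic timing, and section 7.7 ties visits to its limits. Because section 7.6 also says Day 75 for the arginine measure, its 3 months may be loose wording for the same admission. This stands. A reader might infer from section 7.6 that these tests have no Day 75 visit at all, and that inference is wrong. What remains is a contradiction between section 7.6 on one side and section 3.1.1 and Appendix 1 on the other.

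A reader might also infer that first-graft function will be overstated. Section 3 says: "Subjects who do not meet criteria for insulin-independence at any time after 75 days following the initial transplantation may be eligible" for a second transplant, so the weakest grafts could be replaced before a 3-month test. The documents do not support this as a general claim. Section 7.5.1 allows a second transplant to be considered only once the 75 ± 5 day visit and its metabolic assessment are complete, and Appendix 1 places the tests at that visit. Selective loss would arise only if a site followed the 3 months of section 7.6 and re-transplanted in between. Nothing in the documents says how often that would happen.

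On Clarke, it is fair to say that section 7.6 does expect the score at Day 75, so the documents conflict; they do not uniformly omit it. The Day 75 endpoint lists in section 3.1.1 and the synopsis leave Clarke out, in line with Appendix 1, so dropping it from the change list in section 3.1.2 would also restore consistency. Even so, the current text cannot stand: the rule that Appendix 1 governs metabolic timing, which rescues FSIGT and CGMS, is what removes the Day 75 Clarke score.

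The reply has no answer on Day 75 retinopathy.

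**Conclusion.** Three contradictions hold, all in secondary, hypothesis-generating or safety endpoints. The arginine test is an exploratory side issue. The primary endpoint visit at 75 ± 5 days is scheduled consistently.

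- **FSIGT and CGMS:** section 7.6 followed literally puts both at Days 82 to 99, at least 2 days outside Days 70 to 80. This assumes calendar months and the ± 7 days of section 7.7. If Appendix 1 is followed, the timing is right.
- **Clarke change:** it is computable for none of the 12 planned subjects if Appendix 1 is followed, and for those who complete the form if a site acts on section 7.6.
- **Day 75 retinopathy:** no photograph is scheduled for any of the 12 subjects under any section.

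These are drafting conflicts with practical consequences for data collection. They do not show a biased estimate, and no direction of bias is claimed.

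**What to change.** 1. In section 7.6, replace 3 months for FSIGT and CGMS with Day 75 ± 5, before any subsequent transplant. For the arginine test, use the 75 ± 15 day window of section 3.1.3. There is no reason to tighten that exploratory test to ± 5 days.
2. In Appendix 1, mark the Clarke survey at Day 75, as section 7.6 already expects. The alternative is to remove Clarke from the change list in section 3.1.2, but then section 7.6 has to be edited as well.
3. In section 3.1.1, delete the 75 ± 5 day time point from the retinopathy endpoint, so that it agrees with the synopsis, section 7.6 and Appendix 1.

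The cost is a few words and one table mark. The Clarke survey adds eight questions at a visit that already takes place, and the FSIGT and CGMS timing is what Appendix 1 already requires.
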